5.9.2 Sample size

The trial will include 1200 subjects as per the table below.

| Endpoints | MRI/US Arm | MicroUS Arm | MRI/MicroUS Arm |
|--------------------------------------|------------|-------------|-----------------|
| Primary – MRI vs. MicroUS | 541 | | 541 |
| Secondary – Fusion Comparison | 358 | - | 358 |
| Minimum Sample Size (N=1082) | 541 | 183 | 358 |
| Proposed Sample Size (N=1200) | 600 | 200 | 400 |
| Proposed Randomization Ratios | 3 | 1 | 2 |

It is not anticipated that additional subjects will be required, however if a subject drops out before the biopsy procedure they may be replaced as described in section 5.8.1.6.

5.9.3 Level of significance and power of the clinical investigation

Assuming a csPCa detection rate of 43% in each group, 1082 subjects are needed for 90% power to demonstrate that the lower bound of the two-sided 95% confidence interval is greater than the 10% non-inferiority threshold.

R and/or MATLAB software were used for sample size calculations.

5.9.4 Expected drop-out rates

Factors affecting possible drop-out rates include the option to withdraw participation at any time.

It is anticipated that a subject's inclination to withdraw at procedure-time will be minimal, as prostate biopsy is indicated clinically.

5.9.5 Pass/fail criteria

The primary outcome of the study will fail if the number of subjects diagnosed with csPCa is more than 10% lower than the number of subjects diagnosed with csPCa in the MRI/US arm. This will be quantified by testing against the lower two-sided 95% confidence interval bound for the difference.

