5.7 Objectives and Hypothesis

5.7.1 Objectives

Primary Outcome: Difference in detection rate of Grade Group > 1 Prostate cancers (csPCa) found using MicroUS + systematic biopsy and using mpMRI/US Fusion + systematic biopsy.

Secondary (powered) Outcome: Difference in detection rate of Grade Group > 1 Prostate cancers (csPCa) found using MicroUS + mpMRI + systematic biopsy vs. mpMRI/US Fusion + systematic biopsy.

Secondary (unpowered) Outcomes:

- Difference in negative predictive value of highest risk score per patient (PI-RADS or PRI-MUS) for prediction of csPCa on biopsy
- Added value of each biopsy technique

- Added value of systematic biopsy over targeted biopsy
- Difference in health economic variables:
 - Procedure time
 - Cost (including MRI scan / MRI Magnet time)
 - Radiologist time
- Patient Satisfaction
 - Subpopulation analysis of men in the MicroUS-only arm with prior MRI vs those without

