5.7.2 Hypothesis

Primary Hypothesis: The micro-ultrasound biopsy procedure is non-inferior to the mpMRI/US fusion biopsy procedure with a threshold of 10% and thus reduce the need for MRI prior to biopsy.

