5.8.1.3 Endpoints

Primary endpoint

Number of men diagnosed with csPCa based on the pathology samples collected during the biopsy procedure through:

- MicroUS samples (targeted and systematic samples taken under microUS imaging only without mpMRI)
- mpMRI/US Fusion samples (targeted and systematic samples taken under conventional ultrasound imaging with mpMRI targets)

Secondary endpoints

As above, with the addition of combined results for men undergoing Fusion biopsy on the microUS system:

- mpMRI/MicroUS samples (targeted and systematic samples taken under microUS imaging with mpMRI)

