5.9 Statistical considerations

5.9.1 Statistical design, method and analytical procedures

Case data will be analyzed using Excel and MATLAB or other standard statistical software package.

Overall number of subjects diagnosed with csPCa in the MRI/US arm will be compared to number of subjects diagnosed with csPCa using microUS targeted and systematic biopsy samples in the MicroUS and MRI/MicroUS arms (i.e. discounting the MRI targeted samples taken after blinding in the MRI/MicroUS arm). A non-inferiority threshold of 10% will be used. Assuming a csPCa detection rate of 43% in each group, 1082 subjects are needed for 90% power.

For the secondary fusion comparison overall number of patients diagnosed with csPCa will be compared between MRI/US Arm and MRI/MicroUS Arm with a non-inferiority threshold of 10%. Assuming a csPCa detection rate of 42% in the MRI/US Arm and 44% in the MRI/MicroUS Arm 358 subjects per group is required for 90% power.

Details of the design are presented in section 5.8.1.

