Data available (see Table 3) on this topic include a large 11-center, 1040-subject registry study performing a direct comparison to mpMRI which concluded that the two techniques provided similar sensitivity and negative predictive value.¹³ Various other single-center studies and meta-analyses have demonstrated similar rates of csPCa detection between mpMRI-guided and microUS-guided biopsy protocols.^{8,11,12,39,45,46}

Table 3 - Recent studies comparing microUS and mpMRI

| Study | Metric | MRI | MicroUS |
|---------------------------------|-----------------------------|-----|---------|
| Klotz et al. ¹³ | Sensitivity | 90% | 94% |
| Wiemer et al. ¹² | csPCa detection | 38% | 44% |
| Lughezzani et al. ¹¹ | csPCa detection | 35% | 35% |
| Socarrás et al. ⁴⁵ | csPCa detection | 28% | 24% |
| Abouassaly et al. ⁸ | Increase in csPCa detection | N/A | 12% |

Calculation of Non-Inferiority Threshold and Expected Detection Rates

The non-inferiority threshold of 10% was determined by expert-consensus from the advisory panel involved in the creation of this protocol, however it is consistent with the improvement in csPCa rates observed in the literature for mpMRI over the previous standard of systematic biopsy (see Table 1). The expected csPCa rates across the three arms of 42-44% were calculated based on pooled data from 414 biopsy naïve subjects with combined microUS and mpMRI biopsy across 4 studies at 7 institutions. This data includes 1 previously published study¹¹ and 3 studies which have been submitted for publication, and correlates well with the data from Table 1.

Evaluation of hazards, risks and safety measures

Risks associated with the biopsy procedure are well understood and outside the scope of this protocol since the biopsy procedure is clinically indicated and study procedures are not expected to modify these risks. Risks associated with study data collection will be managed by the Study Monitor, as described in this CIP.

Statistical and weighting methods

All clinical studies were weighted based on enrollment numbers, unless otherwise stated or specifically excluded for differences in protocol or enrollment. Care was taken to identify studies with patients drawn from the same population which would not be independent.

Conclusions

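### The primary pass/fail rule in 5.9.5 is worded as a 10% drop in the number of men diagnosed, and 5.9.3 omits the minus sign, whereas the trial is sized on an absolute margin of 10 percentage points in detection rate

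*Combined protocol and SAP*

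**What the plan says.** The protocol and SAP describe the primary comparison in several places, and the wording differs.

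- **5.7.1 Objectives:** the primary outcome is "Difference in detection rate of Grade Group > 1 Prostate cancers (csPCa) found using MicroUS + systematic biopsy and using mpMRI/US Fusion + systematic biopsy". This is a difference between rates.
- **5.7.2 Hypothesis and 5.9.1:** both give a 10% threshold without a scale; 5.9.1 says only "A non-inferiority threshold of 10% will be used". Section 5.9.1 does name the groups: the MRI/US arm against micro-ultrasound sampling in the MicroUS and MRI/MicroUS arms together, leaving out the MRI-targeted cores in the latter.
- **5.8.1.3 Endpoints:** the primary endpoint is "Number of men diagnosed with csPCa based on the pathology samples collected during the biopsy procedure through" each sampling route. This is a count.
- **5.9.3:** success means that "the lower bound of the two-sided 95% confidence interval is greater than the 10% non-inferiority threshold". There is no minus sign.
- **5.9.5 Pass/fail criteria:** the primary outcome fails if "the number of subjects diagnosed with csPCa is more than 10% lower than the number of subjects diagnosed with csPCa in the MRI/US arm". A second sentence says that this is tested with the lower bound of the two-sided 95% interval for the difference. The group compared with MRI/US is not named.
- **5.9.6 (termination criteria):** the final one-sided significance level drops from 0.025 to 0.024 because of the interim look.
- **5.20:** the margin came from expert consensus, and "it is consistent with the improvement in csPCa rates observed in the literature for mpMRI over the previous standard of systematic biopsy". The Table 1 differences cited there are differences between percentages, for example 53% against 48% giving 5%.

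No section calls the margin absolute or relative, expresses it in percentage points, or writes it as -10%.

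**The concern.** Section 5.9.5 is where the verdict on the primary claim is fixed, and its plain wording does not match the rule behind the sample size. One number being 10% lower than another is a relative statement. At a 43% detection rate, a relative 10% is 4.3 percentage points, less than half of a 10-point margin. A count also has no denominator, so the comparison is meaningful only if the groups analysed are equal in size. Sections 5.9.9 and 5.9.11 drop withdrawn, incomplete and inconsistent records, so equality is not guaranteed.

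At stake is whether a reported pass can be defended against the written criterion. A result that clears -10 points but not a relative 10% could be called a success under 5.7.1 and a failure under 5.9.5. The interim stop in 5.9.6 depends on the same primary objective being proven, so it inherits the ambiguity.

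**Working it through.** **Inputs.** Detection rate 43% in both groups, 90% power, 1082 subjects (5.9.1, 5.9.3). Minimum 541 v 541 and proposed 600 v 600, with 600 = 200 MicroUS + 400 MRI/MicroUS (5.9.2). Fusion comparison 42% v 44%, 358 per group (5.9.1). Final one-sided alpha 0.024 (5.9.6). All calculations use the normal approximation.

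**Step 1: which margin reproduces the stated sizes?**

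n per group = [p1(1-p1) + p2(1-p2)] × (z_alpha + z_power)² / (margin - (p_control - p_test))²

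- Primary, margin 0.10, alpha 0.025: 0.4902 × (1.960 + 1.282)² / 0.10² = 515.1, so 516; with continuity correction, 535.
- Primary, margin 0.10, alpha 0.024: 520.6, so 521. With continuity correction, (n/4)[1 + √(1 + 4/(0.10n))]² = 540.4, so 541. This is the plan's figure exactly (2 × 541 = 1082).
- Fusion, margin 0.10, alpha 0.025, no correction: 0.4900 × (1.960 + 1.282)² / 0.12² = 357.5, so 358. This is again exact.
- Primary, relative margin of 10% (0.10 × 0.43 = 0.043): about 2,510 to 2,786 per group, depending on whether a ratio or a difference is tested.

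The documents do not state the formula, so the alpha and continuity correction behind each figure are inferred. Under any of these choices, only an absolute 10-point margin comes near the planned sizes.

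**Step 2: identical observed rates of 43%.**

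SE = √(2 × 0.43 × 0.57 / n); lower 95% bound = 0 - 1.96 × SE.

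| | 541 v 541 | 600 v 600 |
|---|---|---|
| Lower bound, points | -5.90 | -5.60 |
| Against -10 points | pass | pass |
| Against -4.3 points (relative 10%) | fail | fail |
| Same bound in men, against allowance | -31.9 v 23.3 | -33.6 v 25.8 |
| Lower bound of rate ratio, against 0.90 | 0.872, fail | 0.878, fail |

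**Step 3: power when the true rate is 43% in both groups.**

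Power = Φ(margin/SE - 1.96). At 600 v 600, SE = 0.0286.

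| Rule | 541 v 541 | 600 v 600 |
|---|---|---|
| Absolute 10 points | 91.3% | 93.8% |
| Relative 10%, fixed at 4.3 points | 29.8% | 32.4% |
| Relative 10%, log rate ratio | 32.5% | 35.4% |

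Any result that passes the relative rule also passes the absolute one. At 600 v 600 the choice of reading would therefore decide the verdict in about 93.8 - 32.4 = 61% of trials of two truly equal methods (58% on the ratio scale).

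**Step 4: sensitivity to the rate.** The results in Step 2 are the same at 42% and 44%. On the difference scale, identical rates would pass the relative rule only above about 56% (600 per group) or 59% (541 per group).

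**Step 5: counts without denominators.** As an illustration only, since the plan gives no drop-out rate: 570 v 600 men analysed at 43% each gives 245 v 258 diagnosed. That is 13/258 = 5% lower with no difference in rate.

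**The case against.** The strongest reply is that the intended rule can be recovered. Section 5.7.1 names a difference in detection rate, 5.20 ties the margin to percentage-point differences, and both sample sizes reproduce on the absolute scale. The second sentence of 5.9.5 refers to an interval for the difference, which permits the absolute reading and already presupposes denominators. With equal planned groups, numbers of men can pass as shorthand for rates. All of this stands, and it makes the fault one of wording.

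It also rules out three stronger readings.

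- *A reader might infer that the plan adopts a relative margin and that the trial is therefore badly underpowered.* It does not say so. The low power belongs to one literal reading of one sentence. Failure at identical rates also requires applying the confidence-bound sentence to that reading, at rates near those planned. On the first sentence alone, identical counts are 0% lower and do not fail.
- *A reader might infer from 5.9.3 that micro-ultrasound must beat MRI by more than 10 points.* The same sentence assumes equal rates, claims 90% power and calls the threshold one of non-inferiority. None of these fits a superiority requirement, so this is an evident sign slip.
- *A reader might infer that the scale is free to be chosen once results are known.* The relative rule is always the stricter, so the only convenient choice would be the absolute rule, to which the published sample size already commits the trial.

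The reply does not remove the need for a correction. The section that states the verdict is the one whose plain words conflict with the rest, and a primary decision threshold should not have to be reconstructed from a sample size calculation.

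**Conclusion.** The point holds as a misworded primary decision rule. Sections 5.9.5 (a relative drop in counts, comparison group unnamed) and 5.9.3 (sign omitted) do not state the rule that 5.7.1, 5.20 and the sample sizes imply, namely a lower bound above -10 percentage points for the difference in detection rate. Taking 5.9.5 as relative together with its interval sentence, at 600 v 600 and rates near 43%, turns a pass at identical rates into a fail and cuts power from about 94% to about 32-35%. These figures assume the plan's own rates, equal groups and the normal approximation. The figure of 1082 is not an error. Because the text is the criterion for the primary claim and applying it as worded gives the wrong answer, it must be corrected before the analysis.

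**What to change.** State one rule, in the same terms, in 5.7.2, 5.8.1.3, 5.9.1, 5.9.3 and 5.9.5:

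- **Endpoint:** the proportion of men with csPCa.
- **Estimand:** the proportion detected by micro-ultrasound targeted plus systematic samples in the pooled MicroUS and MRI/MicroUS arms, minus the proportion detected in the MRI/US arm.
- **Decision:** non-inferiority is shown if the lower confidence bound for this difference exceeds -10 percentage points (absolute).
- **Confidence level:** matched to the final one-sided alpha of 0.024 in 5.9.6. That is a two-sided interval of 1 - 2 × 0.024 = 95.2%, in place of the 95% now in 5.9.3 and 5.9.5.

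State the fusion comparison (MRI/MicroUS minus MRI/US) on the same absolute scale. The cost is a few sentences in five short sections. Sample size and data collection do not change: at 600 v 600, power under the absolute rule is 93.8% at alpha 0.025 and 93.6% at 0.024.

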5.9.6 Criteria for the termination of the clinical investigation

The investigation may stop early for success if the primary objective is proven with $p < 0.0026$ at an interim analysis performed at 50% recruitment. This was calculated using O'Brien-Fleming bounds, and lowers the maximum p-value at final analysis from 0.025 to 0.024.

If the investigation is terminated early, no follow-up with subjects is required, since the standard of care for patients anticipating prostate biopsy is not affected by early termination.

5.9.7 Procedures for reporting deviation from the statistical plan

Where the analysis of case data does not handle unexpected data, Exact Imaging in conjunction with the Principal Investigators and 3rd party biostatistician will establish a strategy to modify the analysis algorithm and apply it to all data. Such modifications will include validation of the algorithm prior to its acceptance for use.

These modifications will be updated and described in the CIP, and/or as in the final report (as appropriate) along with justification for them.

5.9.8 Specification of subgroups for analysis

A subgroup analysis is planned for men in the MicroUS arm of the study who deviate from protocol by having prior mpMRI available. This analysis will be used to demonstrate whether or not this group is consistent with the group of men in the MicroUS arm who are mpMRI naïve.

5.9.9 Procedures that take into account all data

Statistical analyses around study endpoints will not include data for subjects who are withdrawn (before or after their biopsy) or for whom the collected study data is incomplete.

5.9.10 Treatment of missing, unused data

If a study subject withdraws from the main trial prior to imaging, his consent form will be retained, and the reason for exclusion of the data will be handwritten on the form as "withdrawn prior to imaging". Similarly, if a study subject withdraws from the main trial following his imaging, his consent form and CRF will be retained, and both will be marked "withdrawn following imaging".

This will allow data to be collected about the number of patients that withdrew from the investigation prior to the imaging procedure, and the number that withdrew after the procedure.

The same process will be applied to any circumstance of incomplete or incorrect data, with an indicator handwritten on his consent form and CRF to provide information about why the record is not used for analysis.

5.9.11 *Exclusion of data*****

Conditions that would result in the exclusion of data would be if any data verification activity showed that data was recorded on the CRF incorrectly, or if the pathology report showed any inconsistency with information on the CRF.

If such incorrect data was discovered, data for this subject will not be included in any analysis, and the CRF for the subject will be marked to indicate that the data is excluded.

5.9.12 *Subjects at multi-center investigations*****

This information is provided in section 5.8.3.7.

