5.8.1.6 Replacing subjects

Case data for all enrolled study subjects will be included in the analyses. Because a subject's involvement ends following biopsy, and because it is not expected that a subject will drop-out after this procedure, the need to replace subjects is expected to be unlikely.

If a subject needs to be replaced, they will be consented as per processes described for all study subjects.

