5.8.3.3 Criteria and procedures for subject withdrawal or discontinuation

Subjects may withdraw from the investigation at any time with no effect on their future care.

If a subject wishes to stop participating in the investigation, they are to do so by notifying the Principal Investigator by phone or letter.

If a subject withdraws from the investigation prior to having his biopsy procedure performed, the procedure will be performed as per the normal standard of care. There will be no further follow-up with this subject in the context of this investigation.

Data considerations for this case are provided in section 5.9.

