5.8.5 Monitoring Plan

A risk-based monitoring plan shall be developed by the sponsor which will be tailored according to the stage of clinical development and the type of clinical investigation.

The sponsor shall ensure, through oversight of the clinical investigation and timely adverse event

reporting, that unanticipated adverse device effects are identified and investigated rapidly so that, where necessary, additional risk control measures can be implemented. With the outcome of the risk assessment, a monitoring plan shall be developed outlining:

- a) the risks associated with the clinical investigation and adequate information on relevant risk control measures;
- b) the processes that need to be monitored including data that is required to be verified in source documents;
- c) the monitoring methods (on-site, a combination of on-site and where justified, centralized monitoring, as appropriate);
- d) the responsibilities;
- e) the procedures and requirements for the investigation's oversight;
- f) the methods for documenting and communicating monitoring results;
- g) the methods for obtaining compliance;
- h) the process for escalation in case of continuous or egregious non-compliance;
- i) those aspects of the clinical investigation which need special attention because if performed incorrectly or inadequately, would compromise the protection of human subjects or the integrity of the data;
- j) special requirements regarding personal data protection.

The Study Monitor role for the clinical investigation will be provided by the sponsor. The sponsor will determine the extent and nature of monitoring for the clinical investigation that will be based on continuing risk assessment. The Study Monitor will adhere to the monitoring responsibilities, which include verifying that:

- a) compliance with the CIP is maintained and any deviation from the CIP is discussed with the clinical investigators, documented and reported to the group of Principal Investigators,
- b) the device is being used according to the CIP, and if modifications are required either to the device or its method of use or to the CIP, this need is reported to the group of Principal Investigators,
- c) the clinical investigators have and continues to have staff and facilities to conduct the clinical investigation safely and effectively,
- d) the clinical investigators have and continues to have access to an adequate number of subjects and devices,

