- e) signed and dated informed consent forms have been obtained from each subject at the time of enrolment and before any study-related procedures are undertaken,
- f) the data in the case report forms are complete, are recorded in a timely manner and are consistent with the source data, the procedures for recording and reporting adverse events and adverse device effects to the sponsor are followed,
- g) there is a process in place for device accountability and traceability and that it is maintained,
- h) maintenance and calibration of the equipment relevant for the assessment of the clinical investigation is performed and documented,
- i) subject withdrawal and/or non-compliance is documented and discussed with the clinical investigator and reported to the group of Principal Investigators,
- j) findings of non-compliance or required modifications shall be reviewed with the investigator and disclosed in a written monitoring report to the group of Principal Investigators.

Source data will be recorded on case report forms (CRFs) as described in section 5.8.6.

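### As written, 5.9.9 and 5.9.11 drop randomised men whose csPCa status is known because of a CRF error, a CRF–pathology mismatch, an incomplete record or withdrawal after biopsy

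*Combined protocol and SAP*

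**What the plan says.** Two sections decide who is removed.

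- **5.9.11** has two triggers: a verification activity shows that a CRF entry is wrong, or "if the pathology report showed any inconsistency with information on the CRF". The consequence is "If such incorrect data was discovered, data for this subject will not be included in any analysis".
- **5.9.9** takes out of the endpoint analyses men who withdraw, before or after biopsy, "or for whom the collected study data is incomplete".

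Section 5.9.10 ("The same process will be applied to any circumstance of incomplete or incorrect data") describes how forms are kept and marked to show why a record was not used. It presupposes exclusion but adds no separate trigger.

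Against these, 5.8.1.6 says "Case data for all enrolled study subjects will be included in the analyses". For men who withdraw before biopsy, 5.8.3.3 defers to the statistical section: "Data considerations for this case are provided in section 5.9". No such cross-reference exists for CRF errors or incomplete records.

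Checking is planned. Under 5.8.5, "The Study Monitor role for the clinical investigation will be provided by the sponsor", and the monitor verifies that "the data in the case report forms are complete, are recorded in a timely manner and are consistent with the source data". Sections 5.8.5.1 and 5.8.6 provide for CRF review and for follow-up of missing, inconsistent or unusual data, and 5.10.2 adds a comparison of CRFs with stored images. None of these sections says that a corrected record stays in the analysis.

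**The concern.** Randomisation is at the consent visit and precedes the biopsy (5.4.6), so every exclusion at issue comes after randomisation. The primary endpoint is read from the biopsy pathology (5.8.1.3), and the same pathology report is one of the triggers for removal. A man with a clear pathology result can leave the primary analysis because of an error elsewhere on his CRF. The rule acts when the error is discovered, so more thorough verification removes more men.

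No section says who decides on a removal, or that the decision is made without knowledge of arm and csPCa result. The third-party biostatistician in 5.9.7 is involved in changing the analysis algorithm, not in keeping or removing a subject. No analysis set, intention-to-treat or other, is defined to settle the difference between 5.8.1.6 and 5.9. Two analysts working from the same document could build different primary populations for the non-inferiority test, both at the interim look and at the end.

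**Working it through.** **Reading the rules side by side**

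| Man's situation, csPCa status known | 5.8.1.6 | 5.9.9 / 5.9.11 |
|---|---|---|
| CRF entry found wrong, then corrected | analysed | out of every analysis (5.9.11) |
| Pathology report and CRF disagree on any item | analysed | out of every analysis (5.9.11) |
| Collected data incomplete in a non-endpoint item | analysed | out of endpoint analyses (5.9.9, on one reading) |
| Withdraws after biopsy | analysed | out of endpoint analyses (5.9.9) |

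**Reproducing the plan's sample size.** Inputs: 43% in each group and margin 10 points (5.9.1, 5.9.3), power 90%, one-sided alpha 0.024 at the final analysis (5.9.6).

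- n = 2 × 0.43 × 0.57 × (1.9774 + 1.2816)² / 0.10² = 520.6 per group.
- With continuity correction, n/4 × [1 + √(1 + 4/(0.10 n))]² = 540.4, rounded up to 541. Twice 541 is 1082, the plan's figure.

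**Effect of exclusions.** The primary comparison is 600 MRI/US against 200 + 400 = 600 microUS-guided men (5.9.2). All exclusion rates below are assumed, because the documents give none. Let e1 and e0 be the exclusion rates in men with and without csPCa, and p the true rate in a group.

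- Retained fraction k = p(1 − e1) + (1 − p)(1 − e0)
- Analysed n = 600k; observed rate = p(1 − e1)/k
- Chance of declaring non-inferiority = Φ[(microUS rate − MRI rate + 0.10)/SE − 1.9774], with unpooled Wald SE and no continuity correction
- Power is taken at 43% vs 43%; type I error at 43% (MRI/US) vs 33% (microUS-guided). The interim look is not modelled.

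Worked case, losses of 6% (csPCa-positive) and 2% (csPCa-negative) in MRI/US only, true rates at the margin:

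- k = 0.43 × 0.94 + 0.57 × 0.98 = 0.9628; n = 577.7; observed MRI/US rate = 0.4042/0.9628 = 0.4198.
- SE = √(0.4198 × 0.5802/577.7 + 0.33 × 0.67/600) = 0.0281.
- (0.33 − 0.4198 + 0.10)/SE = 0.362; Φ(0.362 − 1.977) = 0.053.

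Worked case, the same losses in the microUS-guided group only, true rates 43% and 43%:

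- SE = 0.0288; (0.4198 − 0.43 + 0.10)/SE = 3.117; Φ(3.117 − 1.977) = 0.873.

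| Assumed exclusions | Power | Type I error |
|---|---|---|
| None | 93.6% | 2.4% |
| 10% of both groups, unrelated to csPCa (540 vs 540) | 91.0% | 2.4% |
| 6% / 2% in MRI/US only | – | 5.3% |
| 6% / 2% in microUS-guided only | 87.3% | – |

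These scenarios are not bounds. If 5% of microUS-guided men were excluded and all were csPCa-negative, the observed rate at the margin would be 0.33/0.95 = 0.347, the apparent difference −8.3 points, and the type I error about 8.6%.

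**The case against.** The strongest reply is that the plan means errors to be found and corrected. Follow-up of inconsistent data has little purpose if every discovered error removes the man for good, and part of the procedure may sit in the separate monitoring plan that 5.8.5 calls for. So 5.9.11 may have been intended only for discrepancies that cannot be resolved. That is a fair reading of the intent, but the text is triggered by discovery, and no section keeps a corrected record.

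Second, 5.8.1.6 is a passage about replacing subjects, whereas 5.9 holds the specific data-handling rules, so an ordinary reading lets 5.9 prevail. This softens the conflict. It does not help with the main problem, because 5.9 is the section that discards known endpoints.

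Third, a reader might infer that an unanswered post-biopsy survey removes a man from the primary analysis, since the survey is listed among the CRF data in 5.8.6. That is one reading only. Section 5.9.9 speaks of analyses around study endpoints, and patient satisfaction is itself an outcome (5.7.1), so an endpoint-by-endpoint reading fits equally well.

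Fourth, exclusions that are equal in the two groups and unrelated to csPCa cost little. This stands: harm to the comparison itself needs exclusions that relate to csPCa differently by group.

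**Conclusion.** The point holds as a defect of the written rule and should be corrected. Sections 5.9.9 and 5.9.11 discard randomised men with a known primary endpoint, one trigger is the source of that endpoint, and nothing blinds the decision. The finding rests on that wording and not on the illustrative figures.

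The documents do not support going further. A reader might infer that the rule favours micro-ultrasound, or that the 5.10.2 comparison with images on the ExactVu system makes exclusions differ by arm. No exclusion rate, by arm or by result, appears anywhere, and the monitor's source verification is not restricted to one arm. Bias could run either way or be negligible. On the assumed rates, the result ranges from a 2.6-point loss of power with no change in type I error (10% lost at random) to a type I error of 5.3% or a power of 87.3% (one-sided losses). All of these depend on the assumed rates, the planned 600 vs 600, and one-sided 0.024 at the final analysis.

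**What to change.** Replace 5.9.11 with:

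> Discrepancies between the CRF and source, including the pathology report, are resolved by documented query, and the CRF is corrected with an audit trail. Decisions on unresolved discrepancies are made blind to arm and csPCa result. No randomised subject is excluded from the primary analysis because of a CRF error; csPCa status is taken from the pathology report.

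Replace 5.9.9, and align 5.8.1.6 and the marking text in 5.9.10, with:

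> The primary analysis includes all randomised men with known csPCa status from the study biopsy, analysed by randomised arm, including men who withdraw after biopsy unless consent to use of data is withdrawn. Data are incomplete for an endpoint only if that endpoint is missing. Missing csPCa status is examined in a tipping-point sensitivity analysis, and exclusions are reported by arm and reason.

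Men with missing csPCa status still fall outside this primary set, which is why the tipping-point analysis is needed. The change should be made before any outcome data are analysed by arm, so that the choice between the two rules cannot depend on the result. The cost is a little more query and analysis work; no extra patients or procedures are needed.
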